8.1.2. Treatments Administered During Open-Label Extension

Allowed doses during the open-label extension are shown in Table 3.

Table 3: Sparsentan Doses Allowed During the Open-Label Extension

Number of Capsules Taken During Double-Blind Period	Initial Dose in Open-Label Extension	Target Dose (Week 114) ^a
1	200	200
2	200	400
4	400	800

^a Tolerability to the initial dose will be assessed after 2 weeks. Patients who tolerate the initial dose will titrate to the target dose after 2 weeks, and patients who do not tolerate the initial dose may continue at the initial dose at the Investigator’s discretion. Doses may be modified at any time throughout the open-label extension for safety/tolerability reasons at the Investigator’s discretion.

Patients who are taking 2 capsules of study medication (ie, 400 mg sparsentan or 150 mg irbesartan) at the end of the double-blind period will initiate treatment in the open-label extension at 200 mg sparsentan for the first 2 weeks of the open-label extension. Likewise, patients who are taking 4 capsules of study medication (ie, 800 mg sparsentan or 300 mg irbesartan) at the end of the double-blind period will initiate treatment in the open-label extension at 400 mg sparsentan for the first 2 weeks of the open-label extension. Following 2 weeks at one-half the double-blind dose (ie, Week 114), the Investigator will evaluate dose tolerance (as defined in [Section 8.1.1](#)) prior to titrating up to the target dose. If the patient is tolerating the dose, the patient will titrate to the target dose at this time. Patients who display asymptomatic blood pressure values ≤100/60 mmHg (patients ≥18 years of age) or ≤90/50 mmHg or are below the 5th percentile for sex and height (whichever is lower in patients <18 years of age) or who present with clinical symptoms of orthostatic hypotension but otherwise tolerate the initial dose will continue without titrating up to the target dose after the Week 114 visit. Patients who completed the double-blind period on 4 capsules of study medication (ie, 800 mg sparsentan or 300 mg irbesartan) and initiate treatment in the open-label

extension on 400 mg sparsentan but do not tolerate this dose will be able to reduce their dose down to 200 mg sparsentan. These patients will be able to titrate up to 400 mg sparsentan or 800 mg sparsentan if the Investigator feels the patient can tolerate these doses. Only 1 level of titration up will be allowed at each visit.

Patients who are taking 1 capsule of study medication (ie, 200 mg sparsentan or 75 mg irbesartan) at the end of the double-blind period will initiate treatment in the open-label extension at 200 mg sparsentan for the first 2 weeks of the open-label extension. Following 2 weeks at 200 mg sparsentan (ie, Week 114), the Investigator will evaluate dose tolerance (as defined in [Section 8.1.1](#)). Patients who are tolerating the initial dose will continue on 200 mg sparsentan at this time, including those who display asymptomatic blood pressure values $\leq 100/60$ mmHg (patients ≥ 18 years of age) or $\leq 90/50$ mmHg or are below the 5th percentile for sex and height (whichever is lower in patients < 18 years of age) or who present with clinical symptoms of orthostatic hypotension but otherwise tolerate the initial dose.

For patients who enter the open-label extension with an eGFR value < 30 mL/min/1.73 m² (ie, at Week 108), any dose titration at Week 114 will be at the Investigator's discretion based on the results of the Week 114 assessments. Patients who do titrate to a higher dose at Week 114 will be contacted by the Investigator at Week 116 to assess tolerance of the higher dose; at the Investigator's discretion, these patients may also come in for an additional visit at this time.

Dose modification is permitted during the open-label extension as presented in [Section 8.3.2](#).

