8.2.3. Preparation and Administration of the Study Medication

Patients will be instructed to take the appropriate quantity of capsules/tablets for their assigned oral dose at approximately the same time each day, preferably prior to the morning meal, except on the day of a study visit during the double-blind period. On the day of each study visit in the double-blind period, including the Day 1/Randomization visit, the patient will take their study medication in the clinic. At the visits (both during the double-blind period and open-label period) specified in [Section 15.1](#), study medication will be administered after the pre-dose PK and biorepository (for biomarker assessments) blood samples have been obtained.

Patients will be instructed to swallow the capsules/tablets whole, and not to open, break, chew, crush, or split the capsule/tablet prior to taking. Patients will also be instructed to avoid drinking or eating anything that contains grapefruit, Seville oranges (bitter oranges often used as marmalade), or starfruit (carambola) throughout the study.

If an on-site visit by the patient is not feasible due to challenges related to the coronavirus disease 2019 (COVID-19) pandemic or other unexpected circumstances, study medication may be transported directly to a patient via a traceable courier and/or shipping provider to ensure uninterrupted treatment, if necessary. Before doing this, sites will be instructed to acquire verbal agreement from the patient, verification of correct shipping address, and the patient's availability to receive the shipment. Confirmation of receipt and the shipping process will be documented in the site source documentation. The patient's identity and personal information will continue to be kept confidential and will not be shared with the Sponsor. Refer to the Pharmacy Manual for additional details.

Patients will be instructed that if they miss a dose of study medication prior to the morning meal, they should take the missed dose the same day as soon as it is discovered that they missed the dose. If study medication is missed for the entire day, they will be asked to note the date of the missed dose. Patients should not take 2 doses on any one day.

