8.3.2. Dose Modification, Reduction, or Discontinuation

Patients who display asymptomatic blood pressure values $\leq 100/60$ mmHg (patients ≥ 18 years of age) or $\leq 90/50$ mmHg or are below the 5th percentile for sex and height (whichever is lower in patients < 18 years of age), or who present with clinical symptoms of orthostatic hypotension (see [Section 9.6](#)) but otherwise tolerate the initial dose will continue after the Week 2 visit (or the Week 114 visit for the open-label extension) without titrating up to the target dose. Patients who do not titrate up to the target dose at Week 2 (or Week 114) may titrate up to that dose at any time, based on evaluation of the Investigator, in consultation with the Medical Monitor as needed. Reductions from the target dose back to the initial dose are permitted at any time after titrating up to the target dose.

Patients weighing > 50 kg at screening who do not tolerate the initial dose for any reason may continue at one-half the initial dose at the Investigator's discretion and in consultation with the Medical Monitor, as needed. Patients weighing ≤ 50 kg at screening who do not tolerate the initial dose for any reason will be discontinued from the study.

In patients with temporary dose interruptions, treatment should be resumed whenever possible (including between visits), and treatment resumption should be considered at every visit following study medication interruption.

Doses may be modified at any time throughout the open-label extension for safety/tolerability reasons at the Investigator's discretion. In addition, after titration to the target dose for the open-label extension, increases above the target doses of 200 mg or 400 mg sparsentan may be considered for patients who, in the Investigator's opinion (and following consultation with the Medical Monitor), would benefit from an increased dose.

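### Protocol Section 8.3.2 names no study period, and read as written it disagrees with Table 3 for patients who do not tolerate their first open-label dose

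*Protocol*

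**What the plan says.** Three places in the current protocol deal with a patient who does not tolerate the initial open-label dose.

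- **Table 3, footnote a (Section 8.1.2).** Such "patients who do not tolerate the initial dose may continue at the initial dose", at the Investigator's discretion. No capsule row or body weight is singled out. The footnote also lets doses be changed at any time for safety or tolerability.
- **Text of Section 8.1.2.** Patients who ended the double-blind period on 4 capsules, started the extension on 400 mg and "do not tolerate this dose will be able to reduce their dose down to 200 mg sparsentan". The text gives no lower step for patients who start on 200 mg.
- **Section 8.3.2, second paragraph.** Patients above 50 kg at screening "who do not tolerate the initial dose for any reason may continue at one-half the initial dose", at the Investigator's discretion with Medical Monitor input as needed. Patients of 50 kg or less "at screening who do not tolerate the initial dose for any reason will be discontinued from the study".

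Section 8.1.2 closes with "Dose modification is permitted during the open-label extension as presented in" Section 8.3.2, and Section 6.2.2 (extension design) refers there as well. Open-label sparsentan comes only as 200 mg and 400 mg tablets (Section 8.1), and patients are told "not to open, break, chew, crush, or split the capsule/tablet prior to taking" (Section 8.2.3).

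**The concern.** A site with a non-tolerating patient at Week 114 would look at Table 3, read the text below it and follow the reference to Section 8.3.2. Depending on where it stops, it may keep the patient on the dose, reduce the dose, or take the patient out of the study. In one group it may find that the reduced dose cannot be dispensed.

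Week 114 is also the first tolerability check on sparsentan for patients who had been randomized to irbesartan. If sites resolve the text differently, patients with the same finding are handled differently, and the open-label exposure and discontinuation summaries then partly reflect how each site read the protocol. A wrong reading may be hard to undo, because Section 6.4.2 does not allow study medication to be resumed once an end-of-treatment visit has been completed.

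**Working it through.** No sample size, power or alpha figure is involved. The check is a comparison of text plus one division.

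**Step 1. Does the second paragraph of Section 8.3.2 reach the extension as written?** Sections 8.1.2 and 6.2.2 both send open-label readers to Section 8.3.2. Its first paragraph uses the term initial dose for Week 2 and, explicitly, for Week 114. Its second paragraph uses the same term with no period attached. Section 8.1.1 gives nearly the same rule but ties it to laboratory changes at Week 2; Section 8.3.2 drops that tie. On its face the paragraph covers both periods.

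**Step 2. Half of each Table 3 initial dose.**

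| Capsules at end of double-blind period | Open-label initial dose | Half | Possible with whole 200 or 400 mg tablets? |
|---|---|---|---|
| 1 | 200 mg | 200/2 = 100 mg | No, and not in Table 3 |
| 2 | 200 mg | 200/2 = 100 mg | No, and not in Table 3 |
| 4 | 400 mg | 400/2 = 200 mg | Yes, and agrees with the Section 8.1.2 text |

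**Step 3. Split by screening weight, because Section 8.3.2 does.**

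| Screening weight and start | Table 3 footnote a | Section 8.1.2 text | Section 8.3.2, paragraph 2 | Result |
|---|---|---|---|---|
| Above 50 kg, 400 mg | May continue | May reduce to 200 mg | May take half (200 mg) | Options differ but do not exclude each other |
| Above 50 kg, 200 mg | May continue | Silent | May take half (100 mg) | Half dose cannot be given |
| 50 kg or less, 200 mg | May continue | Silent | Must be discontinued | Direct contradiction |

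Table 3 is arranged by capsule count and Section 8.3.2 by screening weight, so one Table 3 row can contain patients under two different rules. By Table 2, 2 capsules is the target dose at 50 kg or less but the reduced dose above 50 kg.

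**Step 4. Does another sentence settle it?** The general permission to modify open-label doses names no dose and does not say that it overrides a mandatory discontinuation. SAP Section 4.2.2 gives no instruction for non-tolerance in the extension.

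**The case against.** The strongest reply is that the second paragraph of Section 8.3.2 is a double-blind rule that lost its label. The evidence is good. The synopsis puts the same two sentences under its double-blind dosing heading and does not repeat them for the extension. Section 8.1.1 has them and Section 8.1.2 does not. SAP Section 4.2.1 (double-blind) mentions the half-initial dose and Section 4.2.2 (extension) does not. Only Table 2 has a half-initial column and weight rows. Where Section 8.3.2 means the extension, in its first and last paragraphs, it says so. On that reading both the 100 mg dose and the forced discontinuation disappear from the extension. This stands as the probable intent. It does not remove the defect, because a site following the cross-reference finds no such limit.

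Second, the footnote and the Section 8.1.2 text are both permissions, so they can coexist. That is right, and no contradiction is claimed between those two.

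Third, the footnote may be describing patients with asymptomatic low blood pressure. They fail the tolerance definition in Section 8.1.1, yet Section 8.1.2 keeps them on the initial dose. This is plausible, although the protocol elsewhere describes those patients as otherwise tolerating the dose, whereas the footnote says that they do not tolerate it. A reader might infer that the footnote is meant to hold patients on a harmful dose. The documents do not support that: the wording is discretionary, and Sections 6.4.1 and 6.4.2 provide for interrupting or permanently stopping study medication.

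**Conclusion.** The passages are inconsistent as written, within a limited scope:

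- At 50 kg or less at screening, permission to continue (footnote a) and mandatory discontinuation (Section 8.3.2) cannot both be followed.
- Above 50 kg with a 200 mg start, meaning patients who ended the double-blind period on 1 or 2 capsules, the Section 8.3.2 option is 100 mg, which cannot be dispensed.
- Above 50 kg with a 400 mg start, there is no conflict.

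The first two findings assume that the second paragraph of Section 8.3.2 applies to the extension, which its wording allows and other sections make doubtful. If it is confined to the double-blind period, what remains is a loosely worded footnote and no stated lower step for patients who start on 200 mg.

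A reader might infer that every non-tolerating entrant faces contradictory orders, or that everyone who starts on 200 mg is directed to 100 mg. Neither follows: the 400 mg instructions are compatible above 50 kg, and Section 8.3.2 never halves the dose at 50 kg or less. Nor are the double-blind efficacy analyses touched, since the Week 112 evaluations are completed before the first open-label dose. The documents give no count of affected patients. The point is a minor-to-moderate wording correction bearing on open-label safety, exposure and discontinuation data.

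**What to change.** State in Section 8.3.2, sentence by sentence, whether each rule applies to the double-blind period, the extension or both. Then reconcile Table 3 footnote a, the Section 8.1.2 text and Section 8.3.2 so that they give the same instruction for each Table 3 row, refer only to doses that can be dispensed, and say whether screening weight matters in the extension. If footnote a is meant for patients who are simply not titrated, it should say so. Which rule applies is for the sponsor to decide; this review takes no view.

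The cost is a wording change at the next amendment or a clarification letter to sites. No analysis needs to be redone.

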8.2. Study Medication

8.2.1. Packaging and Labeling

For the double-blind period, blinded size 00 capsules will be provided in country-specific labeled 150-cc wide-mouth, round, white, high-density polyethylene bottles with polypropylene caps. Each 68-count bottle will have a label that will contain, but will not be limited to, the following: Sponsor's name and address, protocol number, packaging job/lot number, name and strength (mg) of study medication (in a blinded manner), medication identification number, patient information, caution statement, directions for use, and storage conditions.

For the open-label extension, sparsentan 200 mg tablets will be provided in country-specific labeled 150-cc wide-mouth, round, white, high-density polyethylene bottles with polypropylene caps. Each 68-count or 30-count bottle will have a label that will contain, but will not be limited to, the following: Sponsor's name and address, protocol number, packaging job/lot number, name and strength (mg) of study medication, medication identification number, patient information, caution statement, directions for use, and storage conditions.

Sparsentan 400 mg tablets may also be used in the open-label extension.

For the open-label extension, at some point during the study, the supply of sparsentan 200 mg and 400 mg tablets will be provided in country-specific labeled 40-cc wide-mouth, round, white, high-density polyethylene bottles with polypropylene caps. Each 30-count bottle will have a label that will contain, but will not be limited to, the following: Sponsor's name and address, protocol number, packaging job/lot number, name and strength (mg) of study medication, medication identification number, patient information, caution statement, directions for use, and storage conditions.

All study medication used in this study will be prepared, packaged, and labeled in accordance with the standard operating procedures (SOPs) of the Sponsor or its designee, Good Manufacturing Practice guidelines, International Council for Harmonisation (ICH) guidelines for Good Clinical Practice (GCP), and applicable national regulations. All labels on the packaging will be in accordance with local regulations. Additional details can be found in the study reference manuals.

8.2.2. Storage

Over-encapsulated sparsentan and irbesartan tablets and open-label sparsentan tablets will be shipped and stored between 20-25°C (68-77°F); excursions between 15-30°C (59-86°F) are allowed. All study medication must be stored at the site in a secure location with limited access. Further guidance will be provided by the Sponsor in a Pharmacy Manual.

8.2.3. Preparation and Administration of the Study Medication

Patients will be instructed to take the appropriate quantity of capsules/tablets for their assigned oral dose at approximately the same time each day, preferably prior to the morning meal, except on the day of a study visit during the double-blind period. On the day of each study visit in the double-blind period, including the Day 1/Randomization visit, the patient will take their study medication in the clinic. At the visits (both during the double-blind period and open-label period) specified in [Section 15.1](#), study medication will be administered after the pre-dose PK and biorepository (for biomarker assessments) blood samples have been obtained.

Patients will be instructed to swallow the capsules/tablets whole, and not to open, break, chew, crush, or split the capsule/tablet prior to taking. Patients will also be instructed to avoid drinking or eating anything that contains grapefruit, Seville oranges (bitter oranges often used as marmalade), or starfruit (carambola) throughout the study.

If an on-site visit by the patient is not feasible due to challenges related to the coronavirus disease 2019 (COVID-19) pandemic or other unexpected circumstances, study medication may be transported directly to a patient via a traceable courier and/or shipping provider to ensure uninterrupted treatment, if necessary. Before doing this, sites will be instructed to acquire verbal agreement from the patient, verification of correct shipping address, and the patient's availability to receive the shipment. Confirmation of receipt and the shipping process will be documented in the site source documentation. The patient's identity and personal information will continue to be kept confidential and will not be shared with the Sponsor. Refer to the Pharmacy Manual for additional details.

Patients will be instructed that if they miss a dose of study medication prior to the morning meal, they should take the missed dose the same day as soon as it is discovered that they missed the dose. If study medication is missed for the entire day, they will be asked to note the date of the missed dose. Patients should not take 2 doses on any one day.

8.3. Dosing Considerations

8.3.1. Dose Selection Rationale

The most relevant data for sparsentan dose selection are provided by the Phase 2 studies in patients with essential hypertension and by the ongoing DUET trial in patients with FSGS.

In the hypertension studies, a clear dose response related to blood pressure was observed in hypertensive patients who achieved blood pressure control after 12 weeks of treatment with sparsentan (200 mg, 400 mg, and 800 mg). In these Phase 2 studies, the 800 mg/day sparsentan dose was significantly more effective in lowering blood pressure and achieving blood pressure control than the maximal dose of the active control (irbesartan 300 mg/day). Treatment with sparsentan up to 800 mg daily for up to 12 weeks was also found to be generally safe and well tolerated in both healthy adults and patients with stage 1 and 2 hypertension.

Preliminary results from the DUET trial are described in more detail in [Section 4](#). In the DUET study, the highest sparsentan dose (800 mg/day) tended to have the most prominent antiproteinuric effect while maintaining an acceptable safety profile.

The PK profiles seen at the end of the double-blind treatment period in DUET have been utilized to examine the effect of sparsentan exposure on the primary efficacy endpoint (ie, the change in UP/C from baseline to the end of the 8-week double-blind treatment phase) and on the change in mean seated blood pressure. These results showed that UP/C decreased with increased sparsentan exposure, while variability in UP/C increased with decreasing sparsentan exposure. In contrast, change in mean seated blood pressure with change in sparsentan exposure appeared minimal. Thus, with less interpatient variability and fewer patients exhibiting a lack of benefit (based on change in UP/C), along with no meaningful difference in blood pressure effect, a dose of 800 mg/day is preferred for the current study.

At the beginning of the blinded treatment period, patients will initially receive one-half of the targeted dose (defined as the initial dose) of both sparsentan and the active control, irbesartan. In addition, patients entering into the open-label extension (following a 4-week interval in which no study medication is taken) will initially receive one-half of the targeted open-label dose. This approach follows common clinical practice to initiate treatment with RAAS inhibitors at doses lower than the maximum dose to prevent adverse reactions and potentially harmful elevations in serum potassium and reductions in GFR.

8.3.2. Dose Modification, Reduction, or Discontinuation

Patients who display asymptomatic blood pressure values $\leq 100/60$ mmHg (patients ≥ 18 years of age) or $\leq 90/50$ mmHg or are below the 5th percentile for sex and height (whichever is lower in patients < 18 years of age), or who present with clinical symptoms of orthostatic hypotension (see [Section 9.6](#)) but otherwise tolerate the initial dose will continue after the Week 2 visit (or the Week 114 visit for the open-label extension) without titrating up to the target dose. Patients who do not titrate up to the target dose at Week 2 (or Week 114) may titrate up to that dose at any time, based on evaluation of the Investigator, in consultation with the Medical Monitor as needed. Reductions from the target dose back to the initial dose are permitted at any time after titrating up to the target dose.

Patients weighing > 50 kg at screening who do not tolerate the initial dose for any reason may continue at one-half the initial dose at the Investigator's discretion and in consultation with the Medical Monitor, as needed. Patients weighing ≤ 50 kg at screening who do not tolerate the initial dose for any reason will be discontinued from the study.

In patients with temporary dose interruptions, treatment should be resumed whenever possible (including between visits), and treatment resumption should be considered at every visit following study medication interruption.

Doses may be modified at any time throughout the open-label extension for safety/tolerability reasons at the Investigator's discretion. In addition, after titration to the target dose for the open-label extension, increases above the target doses of 200 mg or 400 mg sparsentan may be considered for patients who, in the Investigator's opinion (and following consultation with the Medical Monitor), would benefit from an increased dose.

